## 64 Study design

65 This study will emulate an investigator-initiated, pragmatic, multicentre, two-arm, open-label, 66 randomised, superiority treatment strategy trial in gout patients initiating ULT for the first time using 67 a cloning, censoring, and weighting approach [11]. Cloning is used to assign people to treatment 68 duration strategies at time zero (i.e., at ULT initiation), eliminating immortal time bias and creating 69 two identical study arms at baseline. Then, a clone is censored when their available data (i.e., the 70 serum urate levels) are no longer compatible with the treatment strategy of the arm they entered, 71 but the follow-up continues for that individual in the arm of the compatible strategy. This induces 72 informative censoring [12], which will be addressed using inverse probability weighting [13].

- The emulation of target trials using real-world data can lead to high-quality evidence and high concordance with randomised controlled trials when closer emulation of trial design and measurements is adopted [14].
- 76

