## 110 Treatment strategies

- 111 Intervention arm (T2T-ULT arm): To emulate ULT initiation aiming to achieve the serum urate target
- 112 of  $\leq$  360 micromol/l within 12 months after ULT initiation, serum urate target will be ascertained by
- 113 the earliest recorded serum urate measurement  $\leq$ 360 micromol/l within 12 months after ULT 114 initiation.
- 115 *Comparison arm (FAF-ULT arm):* Emulation of ULT initiation without an aim to achieve a serum urate
- 116 target will use patients without any recorded serum urate measurements or with serum urate >360
- 117 micromol/l within 12 months after ULT initiation.
- 118 Previous randomised controlled trials showed that the serum urate target can be achieved within 6
- 119 months from the first ULT prescription [1,22,23]. However, the proportion of patients achieving the
- 120 serum urate target in clinical practice is expected to be lower [2]. Therefore, we will allow 12 months
- 121 of grace after ULT initiation for participants to achieve the serum urate target.
- 122

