### 148 Follow up

- 149 People will be followed up from the first ULT prescription to the earliest date of a cardiovascular
- event, transfer out of the primary-care practice, death, 5 years from the first ULT prescription, studyend, and last consultation in primary care.
- Artificial censoring will be applied as follows: 1) clones assigned to the T2T-ULT arm will be censored at 12 months from ULT initiation if they do not achieve the serum urate target, 2) clones assigned to the FAF-ULT arm will be censored at the time they achieve the serum urate target within 12
- 154 to the FAF-OLT and will be censored at the time they achieve the seruin drate target v
- 155 months after the first ULT prescription.
- 156

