## 157 Covariates

- We will collect the following covariates ascertained on or before ULT initiation to build the inverseprobability of censoring weighting as detailed above:
- demographics: age, sex (male or female), latest body mass index (BMI) available only in CPRD,
   socioeconomic deprivation assessed using the index of multiple deprivation (IMD) at patient
- socioeconomic deprivation assessed using the index of multiple deprivation (IMD) at patient
   level in CPRD and income and educational level in VEGA, latest smoking status (current, past, or
- non-smoker) available only in CPRD, latest alcohol intake (current, past, or no intake) available
   only in CPRD. Demographic variables will be ascertained within the 5 years before ULT initiation,
- 165 gout-related variables: gout duration (years), presence of subcutaneous tophi, number of anti-
- 166 inflammatory prescriptions (colchicine, NSAIDs, and corticosteroids) in 12 months before ULT
- 167 initiation, number of consultations in primary care for gout and number of hospitalisations for

- gout in the 12 months before ULT initiation, ULT molecule (i.e., febuxostat, allopurinol,
   uricosurics) and dose (high vs low starting dose), co-prescription of gout flare prophylaxis with
   colchicine and/or non-steroidal anti-inflammatory drugs on the date of ULT initiation (i.e.,
   prescription length ≥21 days);
- 172 general health and other cardiovascular comorbidities: Charlson Comorbidity Index [28], 173 cardiovascular comorbidities not included in the Charlson Comorbidity index (i.e., hypertension, 174 atrial fibrillation, and hypercholesterolemia), heart failure, diabetes with and without target 175 organ damage, chronic kidney disease (stage 3,4,5), dementia, peripheral vascular disease, 176 COPD, cancer, HIV/AIDS European Society of Cardiology cardiovascular risk (high/very high vs 177 moderate/low), history of cardiovascular events before ULT initiation, number of consultations 178 in primary care for any reason and number of hospitalisations for any cause in the 12 months 179 before ULT initiation,
- 180 medications (low-dose acetylsalicylic acid (ASA), non-ASA antiplatelet agents, statins, fibrates,
- other lipid-lowering agents, potassium-sparing diuretics, thiazides, loop diuretics, beta-blockers,
   calcium-channel blockers, angiotensin-converting enzyme inhibitors and angiotensin receptor

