### 188 Statistical analysis

- 189 All descriptive statistics will be reported as number (percentage), mean (standard deviation (SD), or
- 190 median (interquartile range (IQR)) as appropriate.
- 191 Although cloning allows us to account for observed confounding at baseline, the artificial censoring 192 introduced is usually informative [12]. The proposed approach to address this problem is to use 193 inverse probability of censoring weighting. The purpose of the weights is to up-weight patients 194 remaining adherent to the protocol so that they represent censored patients, and as such, maintain 195 the comparability of the study arms throughout the grace period. Survival curves will be estimated 196 using a non-parametric Kaplan-Meier estimator weighted for the inverse probability of censoring 197 weights. The 95% confidence intervals for the difference in 5-year survival and the difference in 198 restricted mean survival times will be obtained using a non-parametric bootstrap with 1000 199 replicates [29].
- 200 First, data from Sweden and the UK will be analysed separately. Then, results will be meta-analysed.
- 201 All analyses will be performed using Stata, version 18 (StataCorp, Texas, USA).

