## 202 Inverse probability of censoring weighing

- In this study, we will estimate the inverse probability of censoring weights by fitting a pooled logistic
   model for the monthly probability of remaining uncensored, including variables for time (in its linear
- and/or quadratic terms depending on the data structure) and the baseline covariates. To avoid
  undue influence of outliers, weights will be truncated at the 99.5th percentile in case of extreme
  weights.
- 208 The inverse probability of censoring weighting will be built using two different models including a
- 209 different set of covariates as shown in the following table.

Variables	Model 1	Model
Age	Y	Y
Sex (male vs female)	Y	Y
Body Mass Index	N	Y
Socioeconomic deprivation	Y	Y
Smoking status	N	Y
Alcohol intake	N	Y
Gout duration (years)	Y	Y
Subcutaneous tophi (y/n)	Y	Y
Number of anti-inflammatory prescriptions (colchicine, NSAIDs, and corticosteroids) in	Y	Y
12 months before ULT initiation		
Number of consultations in primary care for gout and number of hospitalisations for	Y	Y
gout in the 12 months before ULT initiation		
ULT molecule (i.e., febuxostat, allopurinol, uricosurics)	Y	Y
ULT dose (high vs low starting dose)	Y	Y
Co-prescription of gout flare prophylaxis with colchicine and/or non-steroidal anti-	Y	Y
inflammatory drugs on the date of ULT initiation (i.e., prescription length ≥21 days)		
Charlson comorbidity index	N	Y
Cardiovascular comorbidities not included in the Charlson Comorbidity index (i.e.,	Y	Y
hypertension, atrial fibrillation, and hypercholesterolemia)		
Acute or chronic ischaemic heart disease, heart failure, diabetes with and without	Y	Y
target organ damage, chronic kidney disease (stage 3,4,5), dementia, peripheral		
vascular disease, COPD, cancer, HIV/AIDS		
History of cardiovascular events before ULT initiation	Y	Y
European Society of Cardiology cardiovascular risk	Y	Y
Number of consultations in primary care for any reason and number of hospitalisations	Y	Y
for any cause in the 12 months before ULT initiation		
Proportion of days covered by ULT between the date of ULT initiation and the end of	Y	Y
the grace period		N N
Low-dose ASA	Y	Y
Non-ASA antiplatelet agents	Y	Y
Statins	Y	Y
Fibrates	Y	Y
Other lipid-lowering agents	Y Y	Y
Potassium-sparing diuretics	Y Y	Y
Thiazides		Y
Loop diuretics	Y	Y
Beta-blockers	Y Y	Y
Calcium-channel blockers	Y Y	Y
Angiotensin-converting enzyme inhibitors	Y Y	Y
Angiotensin receptor blockers		Y
Other anti-hypertensive agents	Y	Y
Nitrates	Y	Y

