Ves, N: no.	Y	Y

211

212 Model 1 will be used to meta-analyse the results from CPRD and VEGA datasets. Model 2 will be

213 used to test the internal validity of the association between exposure and outcome and to check

whether the variables available only in CPRD could represent major confounders.

215 Missing data

216 BMI, smoking status, alcohol intake status, and socioeconomic deprivation can have missing data in

217 CPRD. The pattern of missingness will be compared and missingness at random assumed. Missing

- 218 data will be imputed using chained equations. BMI, smoking status, alcohol intake status, and
- 219 socioeconomic deprivation will be modelled using multinomial logistic regression.
- 220 Subgroup analyses
- 221 We will perform some sensitivity analyses to test the robustness of the association between the 222 exposure and the outcome.
- We will consider a SU target of ≤300 micromol/l to define the T2T-ULT arm and we will compare
   it with not achieving a SU target of ≤360 micromol/l,
- 225 We will further censor the follow-up when people will discontinue ULT,
- We will exclude from the FAF-ULT arm, those patients who will not have measured serum urate
   levels within 12 months after ULT initiation.
- 228 Also, we will stratify the analyses using the following prognostic factors:
- 229 Age (>65 and ≤65 years),
- 230 Gender (male and female).
- 231 Feasibility count and sample size considerations
- 232 In a previous study, we identified 96,000 patients with incident gout in CPRD. Of them, 48%

233 (~46,000) were ever prescribed ULT, and 28% (~12,000) and 16% (~7,000) achieved serum urate

- targets of  $\leq$ 360 micromol/l and  $\leq$ 300 micromol/l within 1 year after the first ULT prescription, respectively [2].
- 236 Approximately, 20,000 patients with an incident diagnosis of gout were ascertained in VEGA. Of
- them, 42% (~8,000) were prescribed ULT [30]. We assume a similar rate of success as in CPRD. Thus,
- data for approximately 14,000 exposed and 30,000 unexposed patients and 8,000 exposed and
- 239 30,000 unexposed patients will be available for the main aim and the secondary aim, respectively.
- Based on these data, our study will have more than 99% power to detect a risk difference of 1/1,000
- person-years assuming a rate of MACE of 17/1,000 person-years [5] in the unexposed and an alphaerror of 0.025.
- 243 Ethics, funding, and patient partner in research involvement

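### The sensitivity analysis that also censors at ULT discontinuation has no weight model able to correct for stopping driven by post-baseline health, so it could be biased

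*Protocol*

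**What the plan says.** The protocol's Subgroup analyses section lists three sensitivity analyses meant to test robustness. One is "We will further censor the follow-up when people will discontinue ULT". Nothing is said there about how this censoring will be weighted.

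The Follow up section gives two artificial censoring rules for the main analysis, both tied to the urate target in the first year. T2T clones are censored "at 12 months from ULT initiation if they do not achieve the serum urate target". FAF clones are censored when they reach the target within that year. Treatment strategies describes the 12 months as a period "of grace after ULT initiation for participants to achieve the serum urate target".

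Study design accepts that such censoring is a problem: it speaks of "informative censoring [12], which will be addressed using inverse probability weighting". Statistical analysis gives the purpose of the weights as maintaining "the comparability of the study arms throughout the grace period".

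The section on inverse probability of censoring weighting specifies one pooled logistic "model for the monthly probability of remaining uncensored, including variables for time" and the baseline covariates, with truncation at the 99.5th percentile. Covariates opens with "We will collect the following covariates ascertained on or before ULT initiation". The covariate table holds one post-baseline entry, "Proportion of days covered by ULT between the date of ULT initiation and the end of" the grace period. No covariate is updated over follow-up.

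**The concern.** The protocol's own principle is that artificial censoring is usually informative and must be weighted. Censoring at discontinuation is artificial too. It can occur in any month up to 60, and whether a patient stops ULT may well depend on what has happened since baseline: a new diagnosis, an admission, a flare, a urate result. Those same events can carry information about MACE risk. If sicker patients stop more often and the arms differ in how much they stop, the patients still observed differ in prognosis between arms even when treatment has no effect.

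The stake is the value of the robustness check. A discrepancy from the main result could be an on-treatment effect or selective stopping, and agreement could be partly accidental. The weights as specified would not separate these.

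**Working it through.** **Step 1. Set the specification against the need.**

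| | Censoring the weights are described for | Added censoring |
|---|---|---|
| Trigger | Urate target reached or not | ULT discontinued |
| Window | Months 0 to 12 | Months 0 to 60 |
| Covariates specified | Time, baseline covariates, days covered to month 12 | None stated separately |
| Possible drivers | Baseline status, early care | Also health after baseline |

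The days-covered entry does not close the gap. It is one value per patient and stops at month 12. For any earlier month it uses information from later than that month, and it partly measures discontinuation itself.

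**Step 2. Put the planned effect on the 5-year scale.** The feasibility section assumes 17 MACE per 1,000 person-years and a difference of 1 per 1,000. Taking 17 against 16:

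- 1 − exp(−0.017 × 5) = 8.15%
- 1 − exp(−0.016 × 5) = 7.69%
- Difference 0.46 percentage points.

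**Step 3. Size the possible bias with no treatment effect.** The protocol gives no discontinuation rates, so every input below is an assumption.

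- All patients start fit and become frail at q = 6% per year.
- Frailty multiplies the MACE hazard h by 2.5. With h = 0.01446 per year the true 5-year risk is 8.3% in both arms.
- Fit patients stop ULT at rate c per year, frail patients at m × c, with m from 1.5 to 3.

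With f and g the fit and frail fractions still under observation:

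- df/dt = −(h + q + c) f
- dg/dt = q f − (2.5h + m c) g
- observed hazard λ(t) = h (f + 2.5 g) / (f + g)
- estimated 5-year risk = 1 − exp(−∫λ dt)

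Everyone is alike at baseline here, so baseline-only weights would change nothing. False risk difference (T2T minus FAF, percentage points):

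| Stopping per year, T2T vs FAF | m = 1.5 | m = 2 | m = 3 |
|---|---|---|---|
| 10% vs 10% | 0 | 0 | 0 |
| 8% vs 10% | 0.02 | 0.03 | 0.05 |
| 10% vs 15% | 0.04 | 0.07 | 0.12 |
| 5% vs 15% | 0.08 | 0.15 | 0.25 |
| 10% vs 30% | 0.15 | 0.25 | 0.36 |
| 5% vs 30% | 0.19 | 0.33 | 0.50 |

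For example, 10% vs 30% with m = 3 gives 8.00% and 7.64%, a difference of 0.36. With m = 1 every entry is 0. Calibrating to 8.15% instead of 8.3% moves no entry by more than 0.01. For modest differences in stopping the bias is 0.02/0.46 = 4% to 0.12/0.46 = 26% of the planned effect. For 3- to 6-fold differences with m of 2 to 3 it is 0.15/0.46 = 33% to 0.50/0.46 = 109%.

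**Step 4. Check whether baseline covariates could rescue it.** A second model, also with assumed inputs, lets 20% of patients have a baseline factor that raises decline, MACE and stopping, and gives decline a 3.5-fold MACE hazard. Weights built on that baseline factor reduce the false difference from 3.12 to 2.20 per 1,000 in the mildest case with unequal, health-linked stopping, and from 11.13 to 10.41 per 1,000 in the most adverse. They remove 0.92/3.12 = 29% and 0.72/11.13 = 6% of it. Correctly specified time-updated weights remove all of it by construction.

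**The case against.** The strongest reply is that this treats silence as a defect. A reader might infer that the weights stop at month 12, or that this analysis will be unweighted. The protocol says neither. The pooled model is for the monthly probability of remaining uncensored, with no end month, and discontinuation fits that wording. The reference to the grace period states the weights' purpose for the two main censoring rules. An unseen SAP could extend the model. All of this stands. What remains is that the protocol does fix the covariate set, and that set is unsuitable for this censoring however long the model runs.

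Second, the covariates are not purely baseline, and several baseline items (comorbidity, prior admissions, ULT molecule and starting dose) may predict stopping. That is correct, and such items would remove part of the bias. They do not reach events after baseline.

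Third, the magnitude rests on assumptions, and the large values need adverse ones. This also stands: equal stopping gives 0 and modest differences give little. The Step 3 figures describe no correction for post-baseline health, which coincides with baseline-only weighting only because that model has no baseline heterogeneity.

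Fourth, where FAF patients stop more, the error runs against T2T and is conservative for a superiority question. True in that scenario, but the sign reverses if T2T patients stop more, and a check biased against T2T could make a real benefit look fragile.

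**Conclusion.** The point holds as a limited one. The protocol adds artificial censoring over up to 5 years and specifies no weight model that could account for stopping driven by health after baseline. The analysis could be biased if stopping is linked to later prognosis and differs by arm. That it would be biased is a stronger reading the protocol does not support, because it gives no stopping rates and no evidence of a difference between arms.

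Under the assumed inputs the false 5-year risk difference is 0 with equal stopping, about 0.02 to 0.12 percentage points for 8% vs 10% or 10% vs 15% per year, and about 0.15 to 0.5 for 3- to 6-fold differences when frailty doubles or triples stopping. The planned effect is about 0.46. A reader might also infer a threat to the main result. There is none: the primary analysis does not censor at discontinuation.

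**What to change.** For this analysis only, add a second monthly model, fitted separately by arm, for the probability of remaining on ULT over the full follow-up. Include time-updated covariates available from the linked records: flares, admissions, new cardiovascular and renal diagnoses, and latest urate. Multiply its weights, truncated as already planned, with the grace-period weights, and refit the model within each bootstrap replicate.

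The cost is more programming, more variable weights and wider intervals in this one sensitivity analysis. The correction also relies on the recorded covariates capturing why patients stop, which should be stated beside the result. The primary analysis needs no change.

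### One sensitivity analysis drops untested patients from the FAF arm only, using 12 months of post-baseline information; this brings back immortal time in that arm and biases the check in a direction that cannot be assumed

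*Protocol*

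**What the plan says.** The exclusion is the third bullet of the sensitivity analyses under Subgroup analyses in the protocol: "We will exclude from the FAF-ULT arm, those patients who will not have measured serum urate" "levels within 12 months after ULT initiation". It names the FAF-ULT arm alone. No matching rule for T2T, no 12-month landmark and no weight for this selection are given.

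Four other parts of the protocol bear on it:

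- **Study design.** Cloning at ULT initiation is credited with "eliminating immortal time bias and creating" "two identical study arms at baseline".
- **Treatment strategies.** In the main analysis the FAF arm includes the never-tested: its emulation of a strategy without a urate "target will use patients without any recorded serum urate measurements or with serum urate >360" micromol/l.
- **Follow up.** Time zero is the first prescription: "People will be followed up from the first ULT prescription to the earliest date of a cardiovascular" event or one of the other listed ends. On artificial censoring, "clones assigned to the T2T-ULT arm will be censored at 12 months from ULT initiation if they do not achieve the serum urate target". An untested T2T clone is therefore kept, with any event, for the whole first year.
- **Inverse probability of censoring weighting.** The weights come from a pooled logistic "model for the monthly probability of remaining uncensored, including variables for time" and baseline covariates. They address censoring, not removal at time zero.

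**The concern.** Whether urate is measured in the year after initiation is unknown at time zero. Selecting on it in one arm means that every remaining FAF patient survived until a test. Take a patient who dies of myocardial infarction in month 3 without a test: the FAF clone disappears and the T2T clone contributes the event. A patient with a non-fatal event who is not tested at any time in the 12 months is lost from FAF in the same way.

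This undoes both properties for which the protocol adopted cloning. It does so in the only listed analysis that addresses the never-tested patients in the FAF arm. These analyses are meant to test robustness, so a biased one could make a sound result look fragile or a weak one look secure.

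**Working it through.** The protocol gives no figure for this analysis, so there is none to reproduce. The benchmark is the effect in its sample size section.

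**Inputs from the protocol.** MACE 17 per 1,000 person-years in the unexposed; difference sought 1 per 1,000 person-years; 5 years of follow-up; testing window 12 months.

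**Assumed inputs (not in the protocol).** Share p tested within 12 months if event-free, 50-70%; share f of MACE that is fatal, 25-35%; non-cardiovascular death 20 per 1,000 person-years; exponential times; no true effect.

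**Step 1, benchmark.** 5-year risk at 17: 1 − exp(−0.085) = 8.15%. At 16: 1 − exp(−0.080) = 7.69%. Difference: 0.46 points.

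**Step 2, only death prevents testing.** With test rate λ = −ln(1 − p), a fatal event at a uniform time in year 1 is preceded by a test with average probability q = 1 − p/λ. The excluded analysis keeps a fraction q of fatal first-year events and a fraction p of people, so fatal first-year risk is multiplied by q/p. Carried to 5 years:

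fall ≈ 0.017 × f × (1 − q/p) × exp(−0.068)

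- p = 0.5: λ = 0.693, q = 0.279, q/p = 0.557. With f = 0.35: 0.017 × 0.35 × 0.443 × 0.934 = 0.25 points.
- p = 0.7: λ = 1.204, q = 0.419, q/p = 0.598. With f = 0.25: 0.017 × 0.25 × 0.402 × 0.934 = 0.16 points.

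This approximation ignores non-cardiovascular death. Simulation with it included, 4 million patients per scenario, gives 0.15-0.25 points.

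**Step 3, tests after a first MACE not counted.** Setting f = 1 in the same formula gives 0.70 points (p = 0.5) and 0.64 points (p = 0.7). Simulation also gives about 0.6-0.7. This needs an assumption that the protocol does not state.

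**Step 4, can the sign change?** Let the test rate become k times higher after a non-fatal event. Such a case is then tested within the year with average probability g = 1 − [exp(−λ) − exp(−kλ)]/[(k − 1)λ], and

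shift ≈ 0.017 × exp(−0.068) × [(1 − f)(g/p − 1) − f(1 − q/p)]

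| k | p = 0.7, f = 0.35 | p = 0.5, f = 0.25 |
|---|---|---|
| 2 | −0.04 points | +0.16 points |
| 3 | +0.05 points | +0.37 points |

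Simulation agrees: about −0.04 to +0.17 for doubling and +0.04 to +0.36 for tripling. A positive shift makes FAF look worse. Baseline selection acts in the same way: a 1% relative difference in MACE rate moves 5-year risk by 0.085 × 0.01 × exp(−0.085) = 0.08 points. Tested patients with a rate 2-3% higher (0.16-0.23 points) would offset the fall in Step 2.

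**Step 5, with cloning and censoring at target.** A separate simulation cloned each patient and censored FAF clones at target, with 28% reaching target (protocol). It assumed 40%, 60% or 80% tested, 30% of MACE fatal, no confounding and no non-cardiovascular death. Simulation error is about 0.05 points. The rows below let only death prevent testing:

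| Scenario | FAF minus T2T, main analysis | After exclusion | Untested censored at month 12 |
|---|---|---|---|
| No effect | −0.05 to +0.01 | −0.25 to −0.29 | −0.06 to +0.05 |
| 16/17 hazard ratio after target | +0.34 to +0.40 | +0.12 to +0.19 | +0.37 to +0.44 |

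The exclusion creates a gap where none exists and removes about half or more of the design effect. Censoring at month 12 restores the main-analysis result.

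**The case against.** **The bullet may be shorthand.** Treatment strategies also describes the FAF arm in terms of patient selection, and Follow up then implements it as censoring. If this bullet is meant the same way, with details in an analysis plan not shown, weighted censoring at month 12 would remove the immortal time. This is possible, but the preceding bullet speaks of censoring and this one of exclusion, so exclusion is the plain reading. If censoring is intended, the sentence still needs changing.

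**The direction is not fixed.** A reader might infer that FAF must look safer, so that a real T2T benefit is bound to be masked. Step 4 shows otherwise: more testing after a non-fatal event, or modestly higher risk among tested patients, can cancel or reverse the shift. This objection stands in full.

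**The larger figure lacks textual support.** A reader might take 0.6-0.7 points as the consequence of the Follow up section, because follow-up ends at a cardiovascular event. That section ends outcome follow-up; it does not say that urate recording stops. The exclusion uses a fixed 12-month window, so a patient with an infarction in month 2 and a test in month 6 stays in FAF. This also stands.

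**It is one of three sensitivity analyses.** True. That limits the weight of the point but does not make the rule sound.

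**Conclusion.** The rule is wrong as written. It conditions one arm at time zero on later information, so the arms are no longer identical at baseline and FAF regains immortal time. That conclusion follows from the text alone.

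The size depends on assumptions. Under no true effect, with the assumed inputs in the working, FAF 5-year risk falls by about 0.15-0.25 points if only death prevents testing, which is one third to one half of the 0.46-point effect sought (0.15/0.46 = 0.33; 0.25/0.46 = 0.54). It reaches about 0.6-0.7 points only if tests after a first MACE are not counted. The sign can reverse, so the check can mask or exaggerate a T2T benefit.

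Nothing here supports a claim that the primary analysis is biased by this rule: it keeps never-tested patients in FAF and is unaffected.

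**What to change.** Replace the exclusion with artificial censoring. Keep every FAF clone from time zero, count events to month 12, and censor at month 12 those with no serum urate recorded by then, mirroring the T2T rule. Add a month-12 censoring weight for this step, estimated from the baseline covariates already listed. Events before month 12 then count in both arms whether or not a test was done, so neither death nor testing after an event can distort the first year. The weight handles differences in risk between tested and untested patients only as far as the measured covariates explain them.

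The cost is one sentence, one extra weight model and slightly wider intervals in this sensitivity analysis. No new data are needed and the primary analysis does not change.
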